Appendix 14 CFIa – Participant Version

Do not reproduce or distribute. The Sponsor will provide sites with all instruments to be completed in this study.

CFI-Acute (CFIa) – Participant Version

Please complete these questions thinking about your current ability (most recent experience) by selecting the response for the one best answer for each question.

1. How often do you have difficulty with your memory?  Never  Rarely  Sometimes  Often  Always
2. How often do others tell you that you repeat questions over and over?  Never  Rarely  Sometimes  Often  Always
3. How often do you misplace things?  Never  Rarely  Sometimes  Often  Always
4. How often must you rely on written reminders?  Never  Rarely  Sometimes  Often  Always
5. How often do you need help from other people to remember appointments, family occasions or holidays?  Never  Rarely  Sometimes  Often  Always
6. How often do you have trouble recalling names, finding the right word or completing sentences?  Never  Rarely  Sometimes  Often  Always
7. How often do you have trouble driving (slowly or too fast, trouble at night, get lost, have accidents)?  Never  Rarely  Sometimes  Often  Always  I do not drive
8. How often do you have difficulty managing money (paying bills, calculating change, completing tax forms)?  Never  Rarely  Sometimes  Often  Always  Does not apply
9. How often do you participate in social activities?  Never  Rarely  Sometimes  Often  Always
10. How often do you have problems with work performance (paid or volunteer)  Never  Rarely  Sometimes  Often  Always  I do not work or volunteer
11. How often do you have trouble following the news or the plots of books, movies or TV shows?  Never  Rarely  Sometimes  Often  Always
12. How often do you have difficulty with activities for example, hobbies, card games, or crafts?  Never  Rarely  Sometimes  Often  Always
13. How often do you get disoriented or lost?  Never  Rarely  Sometimes  Often  Always
14. How often do you have difficulty using your usual household appliances (such as washing machine or microwave) or familiar electronic devices (computer or cell phone)?  Never  Rarely  Sometimes  Often  Always

CFI-Acute – Participant version, adapted from ADCS-CFI – Participant, Version 3, US-English, 17Sept2015

Used with permission from the NIA-funded Alzheimer's Disease Cooperative Study (NIA Grant U19 AG10483).

REFERENCES

Appendix 15 CFIa – Study Partner Version

Do not reproduce or distribute. The Sponsor will provide sites with all instruments to be completed in this study.

CFI-Acute (CFIa) – Study Partner Version

Please complete these questions without asking the study participant's opinion. You may ask other family members, friends or colleagues of the participant. Select the one best answer for each question thinking about the participant's current ability (most recent experience).

1. How often does the participant have difficulty with memory?  Never  Rarely  Sometimes  Often  Always
2. How often does the participant repeat questions over and over?  Never  Rarely  Sometimes  Often  Always
3. How often does the participant misplace things?  Never  Rarely  Sometimes  Often  Always
4. How often must the participant rely on written reminders?  Never  Rarely  Sometimes  Often  Always
5. How often does the participant need help from other people to remember appointments, family occasions or holidays?  Never  Rarely  Sometimes  Often  Always
6. How often does the participant have trouble recalling names, finding the right word or completing sentences?  Never  Rarely  Sometimes  Often  Always
7. How often does the participant have trouble driving (slowly or too fast, trouble at night, gets lost, has accidents)?  Never  Rarely  Sometimes  Often  Always  Does not drive
8. How often does the participant have difficulty managing money (paying bills, calculating change, completing tax forms)?  Never  Rarely  Sometimes  Often  Always  Does not apply
9. How often does the participant participate in social activities?  Never  Rarely  Sometimes  Often  Always
10. How often does the participant have problems with work performance (paid or volunteer)?  Never  Rarely  Sometimes  Often  Always  Does not work or volunteer
11. How often does the participant have trouble following the news or the plots of books, movies or TV shows?  Never  Rarely  Sometimes  Often  Always
12. How often does the participant have difficulty with activities for example, hobbies, card games, crafts?  Never  Rarely  Sometimes  Often  Always
13. How often does the participant get disoriented or lost?  Never  Rarely  Sometimes  Often  Always
14. How often does the participant have difficulty using usual household appliances (such as washing machine or microwave) or familiar electronic devices (computer or cell phone)?  Never  Rarely  Sometimes  Often  Always

CFI-Acute – Study Partner version, adapted from ADCS-CFI – Study Partner, Version 3, US-English, 17Sept2015

Used with permission from the NIA-funded Alzheimer's Disease Cooperative Study (NIA Grant U19 AG10483).

Appendix 16 Geriatric Depression Scale–30

Do not reproduce or distribute. The Sponsor will provide sites with all instruments to be completed in this study.

Geriatric Depression Scale (GDS) 30-Item Version

Instructions for the interviewer: Read each of the following questions verbatim to the subject and mark (✓) either Yes or No based on the subject's response to each question. Provide the following instruction to the subject before asking the first question: "Choose the best answer for how you have felt over the past week:"

Question	Response	
1. Are you basically satisfied with your life?	 yes	 NO
2. Have you dropped many of your activities and interests?	 YES	 no
3. Do you feel that your life is empty?	 YES	 no
4. Do you often get bored?	 YES	 no
5. Are you hopeful about the future?	 yes	 NO
6. Are you bothered by thoughts you can't get out of your head?	 YES	 no
7. Are you in good spirits most of the time?	 yes	 NO
8. Are you afraid that something bad is going to happen to you?	 YES	 no
9. Do you feel happy most of the time?	 yes	 NO
10. Do you often feel helpless?	 YES	 no
11. Do you often get restless and fidgety?	 YES	 no
12. Do you prefer to stay at home, rather than going out and doing new things?	 YES	 no
13. Do you frequently worry about the future?	 YES	 no
14. Do you feel you have more problems with memory than most?	 YES	 no
15. Do you think it is wonderful to be alive now?	 yes	 NO
16. Do you often feel downhearted and blue?	 YES	 no
17. Do you feel pretty worthless the way you are now?	 YES	 no
18. Do you worry a lot about the past?	 YES	 no
19. Do you find life very exciting?	 yes	 NO
20. Is it hard for you to get started on new projects?	 YES	 no

Appendix 16: Geriatric Depression Scale–30

21. Do you feel full of energy?	 yes	 NO
22. Do you feel that your situation is hopeless?	 YES	 no
23. Do you think that most people are better off than you are?	 YES	 no
24. Do you frequently get upset over little things?	 YES	 no
25. Do you frequently feel like crying?	 YES	 no
26. Do you have trouble concentrating?	 YES	 no
27. Do you enjoy getting up in the morning?	 yes	 NO
28. Do you prefer to avoid social gatherings?	 YES	 no
29. Is it easy for you to make decisions?	 yes	 NO
30. Is your mind as clear as it used to be?	 yes	 NO
TOTAL SCORE (0-30):		_____

Scoring: The GDS Total Score is the sum (1 point each) of the responses in **BOLD, ITALIC, CAPITALS**.

- Items 1, 5, 7, 9, 15, 19, 21, 27, 29, and 30 → score 1 point if the response is “**NO**”.
- Items 2, 3, 4, 6, 8, 10, 11, 12, 13, 14, 16, 17, 18, 20, 22, 23, 24, 25, 26, and 28 → score 1 point if the response is “**YES**”.

REFERENCES

Appendix 17 Alzheimer's Disease Clinical Global Impression of Cognitive Function – Severity (AD-CGI-S)

Do not reproduce or distribute. The Sponsor will provide sites with all instruments to be completed in this study.

Clinician Global Impression of Cognitive Function (CGI-S)

Instructions for the rater: This form is intended to capture a clinician global impression of severity (CGI-S). Please read carefully through the descriptive language for each anchor and on the last page choose the descriptor that best fits the participant's current status.

Clinician Global Impression of Cognitive Function (CGI-S) – Descriptors

1 No problems: The participant has no cognitive problems and appears to have no concerns about his/her current cognitive abilities. He/She is able to perform all activities as usual, without any problems or changes.

2 Minor but noticeable cognitive problems that do not require modifications to his/her daily activities: The participant experiences minor cognitive problems that cause some concern (e.g. occasional forgetfulness, losing his/her train of thought, feeling overwhelmed making plans or decisions). However, he/she is still able to perform all his/her daily activities as usual, without difficulties or need to rely upon additional reminders or help.

3 Minor cognitive problems that require minor modification to daily activities, but he/she is functionally independent: The participant has minor cognitive problems that impact his/her ability to perform certain activities of daily living (e.g. it takes more effort or longer to perform certain activities like paying bills, calculating the tip at a restaurant, and organizing his/her daily schedule) and/or the participant needs to make minor lifestyle changes (e.g. He/she takes additional steps that were not needed before to complete activities, such as writing notes, reminders, or lists). However, he/she is still able to perform all of his/her daily activities independently, without any additional help.

4 Mild cognitive problems with functional impairment noticeable and needs some support: The participant has mild cognitive problems that mean he/she needs support with some activities that he/she used to be able to carry out independently (e.g. taking care finances, going shopping, or the participant had to retire early because of memory/thinking problems) and/or the participant has given up some activities due to his/her cognitive problems (e.g. driving or hobbies).

5 Moderate cognitive problems and functionally dependent outside home: The participant needs help for many daily activities (e.g. dressing and/or personal hygiene) and has stopped other activities due to his/her cognitive problems. He/She is no longer independent in his/her daily activities outside of his/her home.

6 Severe cognitive problems and functionally dependent in daily activities inside and outside home: The participant cannot perform his/her daily activities in his/her own home due to cognitive problems. He/She depends on others for some or all activities of daily life including eating, showering or bathing, dressing, toileting.

Appendix 17: Alzheimer's Disease Clinical Global Impression of Cognitive Function – Severity (AD-CGI-S)

Please rate the severity of the study participant's cognitive problems and the impact on his/her daily activities at this time:

1	No problems	
2	Minor but noticeable cognitive problems that do not require modifications to his/her daily activities	
3	Minor cognitive problems that require minor modification to daily activities, but he/she is functionally independent	
4	Mild cognitive problems with functional impairment noticeable and needs some support	
5	Moderate cognitive problems and functionally dependent outside home	
6	Severe cognitive problems and functionally dependent in daily activities inside and outside home	

Adapted from Guy W, editor. ECDEU Assessment Manual for Psychopharmacology. 1976. Rockville, MD, U.S. Department of Health, Education and Welfare

**Appendix 17: Alzheimer's Disease Clinical Global Impression of Cognitive Function –
Severity (AD-CGI-S)**

REFERENCE

Guy W, editor. ECDEU Assessment Manual for Psychopharmacology. 1976. Rockville, MD, U.S. Department of Health, Education and Welfare.

Appendix 18 Alzheimer's Disease Participant Global Impression of Cognitive Function (AD-PGI-S)

Do not reproduce or distribute. The Sponsor will provide sites with all instruments to be completed in this study.

Participant Global Impression of Cognitive Function (PGI-S)

Instructions for the interviewer: Please ensure that a paper copy of the scale, specifically the response options and descriptions, is in front of the participant. Read out loud all six response categories to the participant, including the full descriptions as displayed on the following pages, before asking the participant to choose the category that best applies to him/her. Enter the participant's response on the last page. Repeat the response categories and detailed descriptions, if necessary, but do not provide alternate examples or additional information.

Appendix 18: Alzheimer's Disease Participant Global Impression of Cognitive Function (AD-PGI-S)

Participant Global Impression of Cognitive Function (PGI-S) – Descriptors

Please rate the severity of any memory/thinking problems you may have had and their impact on your daily activities over the past 7 days:

1 No problems:

I have no memory and/or thinking problems and have no concerns about my current thinking abilities. I am able to perform all my activities as usual, without any problems or changes.

2 Minor but noticeable thinking problems that do not require changes to daily activities:

I experience minor memory and/or thinking problems that cause some concern (e.g. occasional forgetfulness, losing my train of thought, feeling overwhelmed making plans or decisions). However, I am still able to perform all my daily activities as usual, without difficulties or the need to rely upon additional reminders or help.

3 Minor thinking problems that require minor changes to daily activities, but I am independent in daily activities:

I have minor memory and/or thinking problems that impact my ability to perform certain activities of daily living (e.g. it takes more effort or longer to perform certain activities like paying bills, calculating the tip at a restaurant, and organizing my daily schedule) and/or I need to make minor lifestyle changes (e.g. I take additional steps that were not needed before to complete activities, such as writing notes, reminders, or lists). However, I am still able to perform all of my daily activities independently, without any additional help.

4 Mild thinking problems that mean I need help with some daily activities:

I have mild memory and/or thinking problems and as a result need help with some activities that I used to be able to carry out independently (e.g. taking care of finances, going shopping, or I had to retire early because of memory/thinking problems) and/or I have given up some activities due to my memory and/or thinking problems (e.g. driving or hobbies).

5 Moderate thinking problems that mean I rely on someone for daily activities outside of my home:

I need help for many daily activities (e.g. dressing and/or personal hygiene) and have stopped other activities due to my memory and/or thinking problems. I am no longer independent in my daily activities outside of my home.

6 Severe thinking problems that mean I rely on someone for daily activities inside and outside of my home:

I cannot perform my daily activities in my own home due to my memory and/or thinking problems. I rely on others for some or all activities of daily life including eating, showering or bathing, dressing, toileting.

Appendix 18: Alzheimer's Disease Participant Global Impression of Cognitive Function (AD-PGI-S)

Please rate the severity of any memory/thinking problems you may have had and their impact on your daily activities over the past 7 days:

1.	No problems	
2.	Minor but noticeable thinking problems that do not require changes to daily activities	
3.	Minor thinking problems that require minor changes to daily activities, but I am independent in daily activities	
4.	Mild thinking problems that mean I need help with some daily activities	
5.	Moderate thinking problems that mean I rely on someone for daily activities outside of my home	
6.	Severe thinking problems that mean I rely on someone for daily activities inside and outside of my home	

FDA. Patient-Focused Drug Development Guidance Public Workshop. Methods to Identify What Is Important to Patients & Select, Develop or Modify Fit-for-Purpose Clinical Outcomes Assessments. 2018

**Appendix 18: Alzheimer's Disease Participant Global Impression of Cognitive Function
(AD-PGI-S)**

REFERENCE

FDA. Patient-focused drug development guidance public workshop: Methods to identify what is important to patients and select, develop, or modify fit-for-purpose clinical outcomes assessments. [resource on the Internet] 2018b. Available from: <https://www.fda.gov/media/116277/download>.

Appendix 19 Alzheimer's Disease Study Partner Impression of Cognitive Function (AD-SPGI-S)

Do not reproduce or distribute. The Sponsor will provide sites with all instruments to be completed in this study.

Study Partner Global Impression of Cognitive Function (SPGI-S)

Instructions for the interviewer: Please ensure that a paper copy of the scale, specifically the response options and descriptions, is in front of the participant. Read out loud all six response categories to the participant, including the full descriptions as displayed on the following pages, before asking the participant to choose the category that best applies to him/her. Enter the participant's response on the last page. Repeat the response categories and detailed descriptions, if necessary, but do not provide alternate examples or additional information.

Roche WN42444

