
 • To evaluate biomarkers of pharmacodynamics of gantenerumab compared with control 	
 • Change in brain amyloid load over time, as measured by amyloid PET in a subset of participants • Change in brain tau load over time, as measured by tau PET in a subset of participants • Change in CSF biomarkers, including, but not limited to, Aβ₁₋₄₂, Aβ₁₋₄₀, NfL, pTau, and tTau in a subset of participants • Change in blood-based biomarkers, including, but not limited to, Aβ₁₋₄₂, Aβ₁₋₄₀, NfL, and pTau in all participants • Change in MRI-derived measurements over time, including, but not limited to, volumetric changes in whole-brain, ventricles, hippocampus, or other structures in all participants
Exploratory Objectives	Corresponding Endpoints

 • To evaluate the efficacy of gantenerumab compared with control on (1) depressive symptoms, (2) clinician-rated, participant-rated, and study partner-rated global impression of overall disease severity, and (3) health-related quality of life 	
 • (1) Change from baseline to Year 4 in the GDS-30 • (2) Change from baseline to Year 4 in the AD-CGI-S, AD-PGI-S, and AD-SPGI-S scales • (3) Change from baseline to Year 4 in the EQ-5D-5L index-based and VAS scores

 • To evaluate the efficacy of gantenerumab compared with control on clinical progression 	
 • Time from randomization to clinical progression to MCI or dementia based on the site clinician's diagnostic classification

 • To characterize the PK profile of gantenerumab 	
 • Trough plasma concentrations of gantenerumab at specified timepoints • PK parameters estimated with population PK modeling

 • To evaluate the potential relationships between drug exposure and the efficacy and safety of gantenerumab 	
 • Relationship between plasma concentration or PK parameters of gantenerumab and PD as well as efficacy endpoints • Relationship between CSF concentration or PK parameters of gantenerumab and safety endpoints

Table 7 Objectives and Endpoints (cont.)

Exploratory Objectives	Corresponding Endpoints

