- Sites must administer the official version of each instrument using the study electronic device, as provided by the Sponsor. Instruments must not be copied from the protocol.
- Sites should allow sufficient time for participants and study partners to complete the instruments
- Sites should administer the instruments in a quiet area with minimal distractions and disruptions
- Participants and study partners should be instructed to answer questions to the best of their ability; there are no right or wrong answers
- Site staff should not interpret or explain questions
- Participants and study partners should not obtain advice or help from others (e.g., family members or friends) when completing the instruments

All cognitive and functional assessments should be performed in the clinic at the visit timepoints indicated in the schedule of activities (Section 1.3). However, in exceptional circumstances for post-randomization visits, if the participant, their study partner or the primary rater cannot perform these assessments as per the schedule of activities, they may be performed within a 28 days' time window (i.e., ± 28 days).

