8.10.2.8 Study Partner Global Impression of Cognitive Function

The AD-SPGI-S is a study partner-reported (ObsRO) global impression of severity measure designed to assess the impact of cognitive impairment on daily function ([Appendix 19](#)). This study-specific AD-SPGI-S was developed in house by the Sponsor for use in clinical trials assessing those at risk for or at the earliest stages of AD (FDA 2018b). The AD-SPGI-S consists of a single item, asking the study partner to rate the severity of their cognitive problems and their impact on the participant’s ability to perform daily activities over the past 7 days (recall period). The item includes six response categories ranging from “no problems” to “severe thinking problems that mean he/she relies on someone for daily activities inside and outside of his/her home”. The item is scored from 0–5 with higher scores indicating more severe cognitive and functional problems. This AD-SPGI-S takes approximately 5 minutes to complete.

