Appendix 19: Alzheimer's Disease Study Partner Global Impression of Cognitive Function (AD-SPGI-S)

Study Partner Global Impression of Cognitive Function (SPGI-S) – Descriptors

Please rate the severity of any memory/thinking problems of your spouse/partner/relative/friend and the impact on his/her daily activities over the past 7 days:

1 No problems:

He/she has no memory and/or thinking problems and appears to have no concerns about his/her current thinking abilities. He/she is able to perform all of his/her activities as usual, without any problems or changes.

2 Minor but noticeable thinking problems that do not require changes to his/her daily activities:

He/she experiences minor memory and/or thinking problems that appear to cause some concern (e.g. occasional forgetfulness, losing his/her train of thought, feeling overwhelmed making plans or decisions). However, he/she is still able to perform all his/her daily activities as usual, without difficulties or the need to rely upon additional reminders or help.

3 Minor thinking problems that require minor changes to daily activities, but he/she is independent in daily activities:

He/she has minor memory and/or thinking problems that impact his/her ability to perform certain activities of daily living (e.g. it takes more effort or longer to perform certain activities like paying bills, calculating the tip at a restaurant, and organizing his/her daily schedule) and/or he/she needs to make minor lifestyle changes (e.g. he/she takes additional steps that were not needed before to complete activities, such as writing notes, reminders, or lists). However, he/she is still able to perform all of his/her daily activities independently, without any additional help.

4 Mild thinking problems that mean he/she needs help with some daily activities:

He/she has mild memory and/or thinking problems and as a result needs help with some activities that he/she used to be able to carry out independently (e.g. taking care of finances, going shopping, or he/she had to retire early because of memory/thinking problems) and/or he/she has given up some activities due to his/her memory and/or thinking problems (e.g. driving or hobbies).

5 Moderate thinking problems that mean he/she relies on someone for daily activities outside of his/her home:

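### The Appendix 19 interviewer instructions for the AD-SPGI-S name the participant, not the study partner, as the respondent, so the wrong person's answer could be recorded

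*Combined protocol and SAP*

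**What the plan says.** **The instruction.** In Appendix 19 the rater places a paper copy of the scale in front of the participant. The rater is then told: "Read out loud all six response categories to the participant, including the full descriptions as displayed on the following pages", and this is to be done "before asking the participant to choose the category that best applies to him/her". The recording step is "Enter the participant's response on the last page".

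**The definition.** Section 8.10.2.8 states: "The AD-SPGI-S is a study partner-reported (ObsRO) global impression of severity measure". It describes a single item "asking the study partner to rate the severity of their cognitive problems". Section 8.10 lists the scale among the observer-reported measures. Table 9 classes the AD-SPGI-S as ObsRO and the AD-PGI-S as PRO.

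**The question on the form.** The stem in Appendix 19 reads: "Please rate the severity of any memory/thinking problems of your spouse/partner/relative/friend and the impact on his/her daily activities over the past 7 days".

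**The endpoint.** The exploratory objective in Section 3 (Table 7) covers "clinician-rated, participant-rated, and study partner-rated global impression of overall disease severity", with change from baseline to Year 4 on each of the three scales.

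**What sites must use.** Section 8.10.1 says: "Sites must administer the official version of each instrument using the study electronic device, as provided by the Sponsor". It adds that instruments are not to be copied out of the protocol.

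**The concern.** The rater is told to put an observer scale to the person being observed. The protocol treats participant and study partner as separate people with separate consent, separate duties and separate questionnaires, so *participant* in Appendix 19 cannot be read as a loose word for whoever is answering.

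What is at stake is the partner's independent view. The exploratory objective lists the partner's rating separately from the participant's because the two can differ, particularly once a participant's insight starts to decline. If the participant answers at some sites or visits and the partner at others, change from baseline mixes two respondents. A wrong respondent at baseline or at Week 211 is enough to spoil the Year 4 change for that participant. The item covers only the past 7 days, so the missing partner rating could not be collected later.

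**Working it through.** No arithmetic applies. The check is a comparison of who answers, and about whom, in each place that says so.

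| Place | Who answers | About whom |
|---|---|---|
| Appendix 19, interviewer instructions | participant | *him/her*, that is, the participant |
| Appendix 19, form title | study partner | – |
| Appendix 19, stem and six descriptors | someone rating a spouse, partner, relative or friend | the participant, in the third person |
| Section 8.10.2.8 | study partner | the participant's cognition and daily activities |
| Section 8.10 and Table 9 | an observer (ObsRO) | – |
| Section 3, Table 7 | study partner | – |
| Appendix 18, interviewer instructions (AD-PGI-S) | participant | *him/her*, that is, the participant |

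1. **Within the instruction.** It refers to the respondent four times: who has the scale in front of them, who is read to, who chooses, and whose response is entered. All four say *participant*. *Study partner* does not occur in it.

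2. **Against Appendix 18.** The two instruction blocks match word for word. In Appendix 18 the wording fits its scale. The likely explanation is that it was carried over to Appendix 19 without adaptation. That is an inference; the documents do not say so.

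3. **Against the other study partner forms.** The EQ-5D-5L proxy form (Appendix 21) tells the interviewer to ask the proxy about the person being assessed. The CFIa partner version (Appendix 15) tells the partner not to seek the participant's opinion. The A-IADL-Q-SV partner version (Appendix 13) is addressed to the partner. Among the partner forms, only Appendix 19 carries participant wording, so participant response was not intended.

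4. **When it is given.** The schedules of activities place the AD-SPGI-S at baseline, Week 105 and Week 211 (Tables 1 and 2 for Q1W, Tables 4 and 5 for Q2W). Tables 1 and 2 also show it at early termination and unscheduled visits. The Year 4 endpoint needs the baseline and Week 211 ratings.

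5. **Who gives it.** Table 9 assigns the AD-PGI-S and the AD-SPGI-S to the same rater role. A rater who follows both instruction blocks literally would put both scales to the participant.

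**The case against.** The strongest reply is that a rater is unlikely to follow the instruction to its literal end. The title names the study partner. The stem asks about someone's spouse, partner, relative or friend, and the descriptors are all in the third person. Section 8.10.2.8 and Table 9 leave no doubt about the intended respondent. Section 8.10.1 requires raters to be trained and approved by the eCOA vendor before giving any scale, and puts the data through an endpoint quality program. All of this stands. It makes the wrong respondent possible rather than certain, but it does not remove the contradiction, and nothing else in the documents corrects it.

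Three stronger readings are tempting and are not supported:

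- **That the field would hold self-ratings duplicating the AD-PGI-S.** The instruction's *him/her* points to a self-rating, but the stem, put to the participant, asks about somebody else, and the AD-PGI-S is worded in the first person. What a participant would be rating is unclear, so duplication does not follow.
- **That the electronic instrument carries the same error.** Sites must use the device version, and it is not in the documents. It may already be correct. What is shown is an error in the protocol appendix.
- **That sites are bound to question the wrong person because staff may not interpret or explain questions.** That rule in Section 8.10.1 concerns explaining items to respondents. It does not stop a trained rater from giving an observer scale to the observer.

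**Conclusion.** The Appendix 19 interviewer instructions are wrong as written. They name the participant as respondent throughout, against Section 8.10.2.8, the ObsRO classification in Section 8.10 and Table 9, and the stem on the same form. Where a rater follows them literally, the participant's answer could be recorded in place of the partner's at any visit where the scale is given.

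The size is small. The AD-SPGI-S is one of three global impression scales under one exploratory objective. It plays no part in the primary PACC-5 analysis, the secondary endpoints or the power calculation. How often the error would occur cannot be estimated from the documents. It depends on the device wording and the rater training, neither of which can be seen, and on how many raters would notice the mismatch. The point is an internal inconsistency to correct, not a question about the choice of scale.

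**What to change.** In the Appendix 19 interviewer instructions, replace *participant* with *study partner* at all four references to the respondent, and replace *applies to him/her* with *applies to the participant*. Then check the electronic version, its translations and the rater training material for the same text, and correct them if it is there.

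The cost is a text correction to one appendix. A device, translation or training update is needed only if the check finds the same wording. Visits, sample size and analysis do not change. If participants have already been assessed with the faulty wording, sites should be asked who answered at those visits, so that ratings given by the wrong person can be identified before the exploratory analysis.
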